1 PROTOCOL SYNOPSIS

Study Title	A Phase 3, Randomized, Single dose, Open-Label Study to Investigate the Safety and Efficacy of OTL38 Injection for Intraoperative Imaging of Folate Receptor Positive Lung Nodules
Protocol Number	OTL-2019-OTL38-007
Sponsor	On Target Labs, Inc. [REDACTED]
Investigational Product	OTL38 Injection: folate analog ligand conjugated with an indole cyanine green-like dye as a solution in vials containing 1.6 mL at 2 mg/mL
Primary Objectives	
1. To confirm the efficacy of OTL38 used with Near Infrared (NIR) fluorescent imaging to detect at least one of the following outcomes in adult subjects scheduled to undergo surgical resection for known or suspected cancer in the lung:
 
[REDACTED]
 
[REDACTED]
 
[REDACTED]
 
[REDACTED]

Secondary Objectives	
The secondary objectives are:
 
 1. To estimate the Sensitivity and False Positive Rate [REDACTED] 2. To estimate the Sensitivity and False Positive Rate [REDACTED] 3. To estimate the Sensitivity and False Positive Rate [REDACTED] 4. To estimate the Sensitivity and False Positive Rate [REDACTED] 5. To evaluate the efficacy of OTL38 used with Near Infrared (NIR) fluorescent imaging to detect a Clinically Significant Event (CSE) in subjects with confirmed cancer in the lung. 6. To estimate the Sensitivity and False Positive Rate [REDACTED]

Exploratory Objectives	
[REDACTED]

Safety Objectives	
1. To assess the safety and tolerability of single intravenous doses of OTL38.2. To assess the safety of the Fluorescence Imaging Systems for intraoperative imaging when used with OTL38.
Study Population	Adult subjects with a suspected primary diagnosis, or at high clinical suspicion of cancer in the lung warranting surgery based on CT and/or PET or other imaging.
Study Design	
This is a phase 3, multi-center, randomized, single dose, open-label study in adult subjects with suspected cancer in the lung scheduled to undergo endoscopic or thoracic surgery per CT/PET or other imaging based on standard of care.
 
[REDACTED]

	
[REDACTED]
 
[REDACTED]
 
[REDACTED]


Treatment
	
 • OTL38 is a folate analog ligand conjugated with an indole cyanine green-like dye. • Each subject will be administered a single intravenous dose of 0.025 mg/kg OTL38. • The imaging systems used in this study do not have market clearance for use with OTL38 and are therefore considered investigational for the purposes of this study. Full specifications for the [REDACTED] [REDACTED] of this protocol. The imaging system used for each subject undergoing fluorescence imaging by the investigational site will be recorded in the eCRF. • Subjects will be evaluated in situ by only one camera. • Subjects will complete a single intravenous dose of OTL38 [REDACTED] [REDACTED]

Study Duration
	
 • Recruitment period is estimated at 18 months • The maximum duration a subject is in the study is 2 months (up to 1month screening; 1month study duration)


Eligibility Criteria
	
Inclusion:
 
 1. Male and Female subjects 18 years of age and older 2. Have a primary diagnosis, or a high clinical suspicion, of cancer in the lung warranting surgery based on CT/PET or other imaging 3. Are scheduled to undergo surgical thoracoscopy for diagnostic wedge resection followed by anatomic lung resection 4. Female subjects of childbearing potential or less than 2 years postmenopausal agree to use an acceptable form of contraception from the time of signing informed consent until 30 days after study completion 5. Ability to understand the requirements of the study, provide written informed consent and authorization of use and disclosure of protected health information, and agree to abide by the study restrictions and to return for the required assessments 
Exclusion:
 
 1. Previous exposure to OTL38 2. Any medical condition that in the opinion of the investigators could potentially jeopardize the safety of the subject 3. History of anaphylactic reactions to folate, including synthetic folic acid (pteroylmonoglutamic acid) and contrast agents containing indocyanine green for near infrared imaging. Subjects with a medical history of ‘idiopathic anaphylaxis’ will require evaluation. 4. History of allergy to any of the components of OTL38, including folic acid 5. A positive serum pregnancy test at Screening or a positive urine pregnancy test on the day of surgery or day of admission for female subjects of childbearing potential 6. Clinically significant abnormalities on electrocardiogram (ECG) at screening. 7. Presence of any psychological, familial, sociological condition or geographical challenges potentially hampering compliance with the study protocol and follow-up schedule 8. Impaired renal function defined as eGFR < 50 mL/min/1.73m² 9. Impaired liver function defined as values > 3x the upper limit of normal (ULN) for alanine aminotransferase (ALT) or aspartate aminotransferase (AST), alkaline phosphatase (ALP), or >2x ULN for total bilirubin except in subjects with Gilbert’s syndrome. 10. Received an investigational agent in another investigational drug or vaccine trial within 30 days prior to the administration of study drug 11. Known sensitivity to fluorescent light

Number of Subjects
	
Up to approximately 130 subjects

Number of Investigator Sites
	
Up to approximately 15 investigational sites

	
[Redacted]
 

[Redacted]	[Redacted]	[Redacted]	[Redacted]	

[Redacted]	[Redacted]	[Redacted]	[Redacted]	

[Redacted]	[Redacted]	[Redacted]	[Redacted]	

[Redacted]	[Redacted]	[Redacted]	[Redacted]	

 
[Redacted]
	[Redacted]															
[Redacted]	[Redacted]	[Redacted]	[Redacted]														
[Redacted]	[Redacted]	[Redacted]	[Redacted]														
[Redacted]	[Redacted]	[Redacted]	[Redacted]														
[Redacted]	[Redacted]	[Redacted]	[Redacted]														

	
[REDACTED]
 
[REDACTED]
 
[REDACTED]
 
[REDACTED]
 
[REDACTED]
 
[REDACTED]
 
[REDACTED]
 
[REDACTED]

Study Endpoints	
Primary
 
The proportion of FAS subjects who have a Clinically Significant Event (CSE). [REDACTED]
 
[REDACTED]
 
[REDACTED]
 
[REDACTED]
 
[REDACTED]
 
[REDACTED]
 
[REDACTED]
 
Secondary
 
The secondary efficacy endpoints are:
 
1. Sensitivity and False Positive Rate [REDACTED] 
a) [REDACTED] 
[REDACTED]

	
b) [Redacted]
 
2. [Redacted]
 
a) [Redacted]
 
b) [Redacted]
 
3. [Redacted]
 
a) [Redacted]
 
b) [Redacted]
 
4. [Redacted]

--	---

	
a) [REDACTED]
 
b) [REDACTED]
 
5. [REDACTED]
 
6. [REDACTED]
 
a) [REDACTED]
 
b) [REDACTED]
 
Safety
 
1. Incidence rates of all treatment-emergent AEs (TEAEs), adverse device effects (ADEs), and SAEs, from the time of OTL38 administration through follow-up Visit 4.2. Evaluation of laboratory parameters (chemistry and hematology) and vital signs3. Evaluation of electrocardiograms (ECG) before and after study drug administration.

Sample Size Estimation
	
Sample Size Estimation
 
[REDACTED]
 
[REDACTED]

	
[REDACTED]

Statistical Methods	
The primary analysis of the CSE primary efficacy endpoint will be a one-sample test for a proportion via an exact binomial test conducted at the two-tailed alpha level of 0.05. [REDACTED]
 
[REDACTED]
 
[REDACTED]
 
[REDACTED]
 
[REDACTED]
 
Analysis of Secondary Efficacy Endpoints
 
The sensitivity endpoints described above will be analyzed [REDACTED]
 
[REDACTED]
 
[REDACTED]
 
[REDACTED]
 
[REDACTED]

Safety	
Safety will be described via subject incidence of treatment emergent adverse events (TEAEs) including serious TEAEs as well as adverse device effects (ADEs). Additionally, summary statistics and/or shift tables will be provided for vital signs, physical exams, ECGs, and laboratory parameters at baseline and post-baseline measurements. All subjects exposed to OTL38 and/or the imaging system will be evaluated for safety and be included in the Safety Analysis Set.

Table of Contents

1 PROTOCOL SYNOPSIS.....4

2 SCHEDULE OF ASSESSMENTS.....14

3 BACKGROUND INFORMATION.....20

3.1 Background.....20

3.2 Rationale.....21

3.3 Investigational Product.....22

3.3.1 Prior Clinical Experience.....22

3 BACKGROUND INFORMATION

3.1 Background

Lung Cancer is the leading cause of cancer related deaths in the United States, with an estimated projection of 142,670 lung cancer related deaths for 2019. Of new cases of cancer, lung cancer is the second most frequent diagnosis, with an estimated projection of 228,150 newly diagnosed cases for 2019 (SEER 2019). Surgery remains the best option for subjects presenting with operable Stage I or II cancers, however the five-year survival rate for these candidates remains concerningly low at 57.4% for localized disease and 30.8% for regional disease (SEER 2019).

The rates of local recurrence suggest that surgeons are unable to completely detect and remove primary tumor nodules. In addition to the primary nodules, local recurrence can also be attributed to synchronous lesions that are not identified on pre-operative imaging and not found during the initial surgery (Chang 2007, Fabian 2011). Positive surgical resection margins (the distance from the primary tumor to the closest resection margin) also contribute to the recurrence rate (Sienel 2007). During video-assisted thoracoscopic surgery (VATS), smaller and deeper nodules are not always identified (Cerfolio 2008, Nakashima 2010). To help identify these smaller or deeper nodules, methods such as CT-guided hookwire, may be useful in identifying the nodule during VATS surgery, but the procedure of inserting the hookwire, can cause severe complications including embolism (Suzuki 2014).

Incomplete resection of non-small-cell lung cancer negatively impacts survival rates (Osarogiabon 2016). Local recurrences are more frequent in patients with segmentectomy than lobectomy (Sienel 2007). The risk of recurrence increases if malignant synchronous lesions are not identified pre-operatively or during surgery and are not removed (Fabian 2011, Yoon 2006). Improved survival after complete resection of synchronous lesions has been shown to be similar to that of complete resection of solitary nodules in node-negative patients. Furthermore, this holds true even when synchronous lesions occur in the ipsilateral lung, or a different lobe, or bilaterally (Chang 2007, Voltolini 2010).

Positive resection margins are often found in many cancer surgeries including lung cancer (Orosco 2018). An increased margin distance has been shown to be associated with a lower risk of local recurrence, with a 10-mm margin distance having a 45% lower recurrence risk than a 5-mm distance (Mohiuddin 2014). In wedge resection for small non-small cell lung cancer, increasing the margin distance less than or equal to 15 mm significantly decreased the local recurrence risk, with no evidence of additional benefit beyond 15mm (Mohiuddin 2014). Therefore, ensuring a negative margin through imaging is important to ensure lower rates of recurrence-free disease and thus, overall survival.

Lung-sparing procedures such as wedge resection or segmentectomy are also important, particularly for patients with poor pulmonary reserve. Furthermore, lobectomy to remove synchronous lesions has not been shown to improve immediate or long-term survival above lung sparing sub-lobar resections (Toufektzian 2014). Intraoperative imaging techniques that increase the accurate identification of cancerous synchronous lung lesions may mitigate the need for unnecessary lobectomy or pneumonectomy.

Intra-operative identification of cancer using real-time imaging modalities that provide tumor identification and demarcation have the potential utility in:

[figure not shown]
- Increasing the possibility of complete removal of cancer without compromising healthy tissue
- Reducing the occurrence of positive resection margins
- Potentially improving overall survival rates
- Improved staging of the tumor.
- Localization of the primary nodule seen on CT/PET
- Removal of additional lesions not previously noted on CT/PET
- Identification of cancerous positive margins of excised tumors

The combination of real-time imaging with tumor-specific fluorescent imaging agents may facilitate optimal resection of lung cancer.

3.2 Rationale

Approximately 85% of lung and pleural malignancies express folate receptor positive nodules (FR+), thus making folate receptors (FR) ideal targets for imaging agents such as OTL-38 (Shen 2015). OTL38 has been observed in preliminary Investigator Initiated studies as being effective in identifying non-malignant lung nodules. These nodules (such as granulomas) do not necessarily pose a threat to the patient's life, but are still targeted for removal by a surgeon to confirm the absence of cancer. Both malignant adenocarcinoma and benign lung nodules that fluoresce in situ are noted to have infiltrates of tumor associated macrophages (TAMs) expressing FR on immunohistochemistry (De Jesus 2015, Shen 2015). Therefore, this intraoperative imaging of lung cancers and nodules would be well-suited in the reduction of positive margins, identification of synchronous lesions, localization of sub-centimeter nodule and tumor tissue, and potentially improving clinical outcomes in these patients. Chemotherapy does not appear to affect FR expression in cancer specimens as examined by immunohistochemistry thus prior treatment is unlikely to affect utility of FR ligands as imaging agents (Crane 2012, Okusanya 2014). Since FR α is normally expressed only in the proximal tubules of the kidneys and in the choroidal plexus, uptake of OTL0038 in the kidneys is possible (Ross 1994). However, the imaging described in this protocol will not involve tissue proximal to the kidneys.

While folate will initially distribute to all cells, redistribution, metabolism, and excretion will eliminate most of this agent from healthy tissues within 2-3 hours. Tumor cells that over expresses FR will retain folate and any fluorescent labeled folate conjugate (Leamon 1993). On Target Laboratories, Inc. has developed OTL0038, a folate analog ligand conjugated with an indole cyanine green-like dye developed by On Target Laboratories, Inc. as a tumor-imaging agent for patients with tumors that overexpress FR.

3.3 Investigational Product

The resulting imaging agent, OTL0038, is the active pharmaceutical ingredient (API) of the drug product, OTL38 Injection (also known as OTL38). All nonclinical studies were conducted with API (drug substance) while clinical studies used OTL38 Injection.

[REDACTED]

The safety profile of OTL0038 has been characterized in a comprehensive series of non-human pharmacokinetic and toxicology studies. The results of the OTL0038 Phase 1-enabling nonclinical safety program in rats and dogs demonstrated the safe use of OTL0038 as an intraoperative imaging agent.

3.3.1 Prior Clinical Experience

OTL has completed the following clinical studies:

- Phase 1a Clinical Study of OTL38 in healthy volunteers, dosed in 23 subjects with a dose range [REDACTED]
- Phase 1b Clinical Study of OTL38 for the intra-operative imaging of folate receptor alpha positive ovarian cancer, dosed in 12 subjects with a dose range [REDACTED]
- Phase 2 Ovarian Clinical Study of OTL38 for the intra-operative imaging of folate receptor alpha positive ovarian cancer, [REDACTED]
- Phase 2 Lung Clinical Study of OTL38 for the intra-operative imaging of folate receptor alpha positive lung cancer, [REDACTED]
- On Target has also initiated an Ovarian Phase 3 Clinical Study of OTL38 for the intra-operative imaging of folate receptor alpha positive ovarian cancer that is currently on-going. [REDACTED]
- [REDACTED]
 - [REDACTED]
 - [REDACTED]

3.3.2 Phase 1a Study of OTL38 Injection in Healthy Volunteers [REDACTED]

This was an ascending dose, randomized, placebo-controlled study in which subjects received a single intravenous (iv) dose of OTL38 [REDACTED]

[REDACTED]

[REDACTED]

3.3.3 Phase 1b Ovarian Cancer Study [REDACTED]

Ten subjects reported a total of 35 adverse events. The most common adverse events were post-surgical wound pain/discomfort, fatigue, abdominal pain/discomfort, nausea and vomiting. All events were graded as mild and all resolved within 1 day of the administration of OTL38. The majority of events were assessed as unrelated by the investigator. The events of nausea and vomiting in the same subject required the administration of an anti-emetic medication (ondansetron).

One subject who received a dose of [REDACTED] OTL38 developed two serious adverse events consisting of post-operative hospital-acquired pneumonia requiring antibiotics and coughing-induced wound dehiscence requiring surgical repair. These events were considered unrelated to OTL38 administration. No deaths occurred during the study.

3.3.4 Phase 2 Ovarian Cancer Study [REDACTED]

[REDACTED]

- [REDACTED]

- [REDACTED]

- [REDACTED]

- [REDACTED]

- [REDACTED]
- [REDACTED]
- [REDACTED]
- [REDACTED]
- [REDACTED]

3.3.5 Phase 2 Lung Cancer Study [REDACTED]

OTL38 injection was evaluated in 100 subjects dosed with 0.025mg/kg with known or suspected lung cancer. [REDACTED]

A summary of safety findings from this study is as follows:

- Most subjects in the Safety population (94/100) had at least one TEAE during the study.
- Study drug infusion was interrupted in 20/100 subjects due to study drug-related AEs (mild-moderate infusion reaction, nausea, vomiting). Infusion was not restarted for 6 subjects with infusion related AEs that were considered related to study drug. These subjects were discontinued from the study. Most AEs resolved the same day.
- The most common TEAEs occurring in subjects were procedural pain (50/100; 50.0%), nausea (33/100; 33%), cough (29/100; 29%), incisional site pain (20%), vomiting (17/100; 17%) pneumothorax (17/100; 17%).
- Most subjects reported TEAEs of grade 2 (moderate) severity (41/100; 41%). Grade 1, grade 3, grade 4 TEAEs were reported by 24%, 25% and 4% of subjects, respectively.
- Most of severe or life-threatening TEAEs were due to post-surgical pain (4/29; 13.8%); hypertension (4/29; 13.8) and pneumonia (3/29 10.3%).
- There were 20 (20%) subjects with a study drug-related TEAE. [REDACTED]

[REDACTED]

- With the exception of the 20 infusion reactions, all TEAEs were typical of those anticipated in the subject population undergoing this type of surgical procedure.
- There were no TEAEs that were considered related to the imaging system.
- There were 14 (14%) subjects with SAEs, none of which were related to study drug. The type and frequency of SAEs was considered consistent with the underlying disease status and medical history of the subjects.
- No subject died during the study.

3.3.6 Other Clinical Experience in Lung and Pituitary Cancer:

[REDACTED]

Please refer to the Investigator’s Brochure for more detailed information on OTL0038 and OTL38 Injection.

3.4 Risks and Benefits of OTL38

3.4.1 Risks

The issues of possible concerns with the use of the OTL38 imaging systems are:

- Presence of an imaging system in the operating room
- Phototoxicity or thermal damage from the light source
- Nonspecific localization of OTL38
- Failure of OTL38 to bind to receptors
- Fading of the chromophore (photobleaching)
- Inability to excite the dye in OTL38 or to record emission
- Adverse events suggestive of hypersensitivity

[REDACTED]

[REDACTED]

[REDACTED]

[REDACTED]

[REDACTED]

[REDACTED]

3.4.2 Benefits

The potential benefits of OTL38 for lung nodule and lesion imaging are:

- Localization of the primary nodule seen on CT/PET
- Increasing the possibility of complete removal of primary nodules and/or cancer without compromising healthy tissue
- Removal of additional lesions not previously noted on CT/PET
- Identification of cancer positive margins of excised tumors
- Reducing the occurrence of positive resection margins
- Improved staging of the tumor.
- Potentially improving overall survival rates

All three CSE components are individually sufficient to identify a clinical benefit as the surgeon would not have been able to identify the CSE by white light and/or palpation alone. Although the use of OTL38 is not intended to change the surgeon's opinion to remove additional tissue based on experience, visualization, or tactile senses, the identification of cancerous lesions identified with NIR alone can lead to improved resection of the cancer and better surgical outcomes.

4 STUDY OBJECTIVES

4.1 Primary

1. To confirm the efficacy of OTL38 used with Near Infrared (NIR) fluorescent imaging to detect at least one of the following outcomes in adult subjects scheduled to undergo surgical resection for known or suspected cancer in the lung:

[REDACTED]

4.2 Secondary

The secondary objectives are:

1. To estimate the Sensitivity and False Positive Rate

[REDACTED]

2. [REDACTED]
3. [REDACTED]
4. [REDACTED]
5. [REDACTED]

[REDACTED]

5 STUDY DESIGN

5.1 Overall Investigation Plan

This is a phase 3, multicenter, randomized, single dose, open-label, pivotal study in patients known or suspected cancer in the lung scheduled to undergo endoscopic or thoracic surgery per CT/PET imaging based on standard of care. This includes wedge resection, lobectomy and thoracotomy and/or completion pneumonectomy.

5.2 Eligibility Criteria

5.2.1 Inclusion Criteria

To be considered eligible to participate in this study, a patient must meet all the inclusion criteria listed below:

1. Male and Female patients 18 years of age and older
2. Have a primary diagnosis, or a high clinical suspicion, of cancer in the lung warranting surgery based on CT/PET or other imaging
3. Are scheduled to undergo surgical thoracoscopy for diagnostic wedge resection followed by anatomic lung resection
4. Female patients of childbearing potential or less than 2 years postmenopausal agree to use an acceptable form of contraception from the time of signing informed consent until 30 days after study completion
5. Ability to understand the requirements of the study, provide written informed consent and authorization of use and disclosure of protected health information, and agree to abide by the study restrictions and to return for the required assessments

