3 OVERALL STUDY DESIGN

This is a phase 3, randomized, multi-center, single dose, open label, pivotal study in subjects known or suspected of having cancer in the lung who are scheduled to undergo endoscopic or thoracic surgery per CT/PET imaging based on standard of care.

[figure not shown]

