4 STUDY POPULATION

The study population will consist of adult subjects with a suspected primary diagnosis, or with high clinical suspicion of cancer in the lung, warranting surgery based on CT and/or PET or other imaging. See Section 5.2 of the protocol for a full list of eligibility criteria.

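### Does inclusion criterion 3 enrol a narrower surgical population than the protocol and SAP say they study?

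*Protocol*

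**What the plan says.** Criterion 3 in Protocol 5.2.1 requires that patients "Are scheduled to undergo surgical thoracoscopy for diagnostic wedge resection followed by anatomic lung resection". The synopsis has the same words, and the opening of 5.2.1 makes every listed criterion compulsory.

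The wider descriptions are these:

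- Protocol 5.1, directly after describing the scheduled surgery as endoscopic or thoracic: "This includes wedge resection, lobectomy and thoracotomy and/or completion pneumonectomy".
- Synopsis, Study Design: subjects "scheduled to undergo endoscopic or thoracic surgery per CT/PET or other imaging based on standard of care".
- SAP section 3: subjects "who are scheduled to undergo endoscopic or thoracic surgery per CT/PET imaging based on standard of care".
- Primary objective (Protocol 4.1, with the same population in SAP 2.1): "adult subjects scheduled to undergo surgical resection for known or suspected cancer in the lung".

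SAP section 4 describes the population in general terms and then defers: "See Section 5.2 of the protocol for a full list of eligibility criteria". The synopsis gives the primary analysis as a "one-sample test for a proportion via an exact binomial test conducted at the two-tailed alpha level of 0.05".

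**The concern.** Criterion 3 joins three conditions: a thoracoscopic procedure, a diagnostic wedge, and an anatomic resection after it. Protocol 5.1 names wedge resection and thoracotomy with no such sequence. Someone reading 5.1 could think a patient booked for open surgery, for a wedge alone, or for resection without a diagnostic wedge was eligible; someone reading 5.2.1 would not. The background adds to the impression of a wider target: "Lung-sparing procedures such as wedge resection or segmentectomy are also important, particularly for patients with poor pulmonary reserve". Criterion 2 also admits patients who already have a diagnosis, for whom a diagnostic wedge may seem unnecessary.

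Two things would be at stake. Sites might apply different rules, with some enrolments counted as deviations. The CSE proportion might also be reported for a wider group than the one enrolled. With a single proportion and no comparison arm in the primary test, the result depends directly on who is in the sample.

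**Working it through.** No formula applies. The sample-size inputs are redacted and no figure in the plan depends on surgical type, so the check is a comparison of texts.

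| Place | Function of the text | Relation to criterion 3 |
|---|---|---|
| Protocol 5.2.1 and synopsis, criterion 3 | Mandatory eligibility rule | The rule itself, identical in both places |
| Protocol 5.1 | Design description naming operations | Wider if the list means stand-alone scheduled operations |
| Synopsis Study Design; SAP 3 | Design description | General; criterion 3 is a subset |
| Protocol 4.1; SAP 2.1 | Objective | General; criterion 3 is a subset |
| Protocol 3.1 | Background on lung-sparing surgery | Says nothing about who is enrolled |
| SAP 4 | Cross-reference | Points to 5.2 as the eligibility list |

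**Step 1: which texts conflict.** A thoracoscopic wedge followed by anatomic resection is one kind of thoracic surgery and one kind of surgical resection. Eligibility criteria ordinarily narrow the general wording of an objective or design summary. Those statements therefore differ from criterion 3 in scope and do not contradict it. Only the list in 5.1 remains as a possible conflict.

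**Step 2: how far 5.1 conflicts.** Its list can be read in two ways.

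- *Steps of one surgical course.* The wedge comes first, then an anatomic resection such as lobectomy, with thoracotomy where it is used. Criterion 3 ties thoracoscopy to the wedge and states no approach for the resection that follows, so an open second stage can satisfy it. On this reading the two sections largely agree.
- *Alternative scheduled operations.* Three plans then fit 5.1 but fail criterion 3: wholly open surgery, wedge alone, and direct resection without a diagnostic wedge.

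The visible text does not choose between the two.

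**Step 3: which text governs.** Protocol 5.2.1 makes all criteria compulsory, the synopsis repeats criterion 3 unchanged, and SAP 4 refers to 5.2. No visible passage gives 5.1 authority over eligibility. If a site did enrol on the strength of 5.1, that would be a departure from 5.2. SAP 9.2 has all deviations listed, and those that define the per-protocol set identified before database freeze.

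**Step 4: effect on the analysis.** The primary endpoint is one proportion in the Full Analysis Set (FAS), tested against a reference value. For a given reference value, the exact binomial calculation does not depend on how widely the surgical population was described elsewhere. The estimate applies to the subjects enrolled, as in any single-population trial.

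**Step 5: size.** An effect would need the mix of planned operations and the CSE proportion within each. Neither is visible, and the CSE definition and reference value are redacted, so neither size nor direction can be stated.

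**The case for a change.** The strongest case for a change rests on 5.1 alone. Its list follows straight on from a phrase about scheduled surgery, so its natural reading is a list of scheduled operations, and it names thoracotomy outright. Up to approximately 15 sites must apply the criteria, and a cross-reference in the SAP does not explain the difference in wording. The protocol also gives some reason to expect the operation to matter. Section 3.4.2 ties a CSE to what the surgeon could not have found by ordinary light or touch, and section 3.1 says that smaller and deeper nodules can be missed during video-assisted surgery. Aligning the wording would cost little.

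Part of this stands. The mismatch between 5.1 and criterion 3 is real on one fair reading, and a wholly open or wedge-only plan does not literally meet criterion 3. Dependence of CSE on the planned operation is plausible but not demonstrated. What does not follow is that sites lack a rule or that the primary analysis is compromised. A table of CSE by planned operation would be an optional extra, and it may already sit in the redacted part of the subgroup list (Protocol 8.2.3, SAP 13.1.2). The synopsis design text, the surgery-day procedures and the FAS and per-protocol definitions are also largely redacted, so the absence of a visible reconciling sentence is weak evidence that the plan has none.

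**Conclusion.** No change to the plan is needed. What remains is one loosely worded descriptive sentence in Protocol 5.1 set against a mandatory criterion that appears identically in two places and to which the SAP defers. Applying 5.2 gives a single eligibility rule, and the one-sample result then describes the population that rule admits. The study report would ordinarily describe that population, including the operations performed.

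The size of any effect on the CSE proportion is unknown from the documents, and no visible number, test or analysis set changes under either reading of 5.1. The conclusion assumes that sites enrol under 5.2, that departures are recorded as SAP 9.2 provides, and that the redacted reference value was chosen for the population 5.2 admits. The visible text does not allow that last point to be checked. Nothing here implies that one surgical scope is preferable to another; that choice belongs to the sponsor.
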